6.4.3 Pilot test

A pilot test will be carried out with at least 2 patients to check the proper collection of variables and debugging of errors in the collection methods and the adequacy of the heating application times and inclusion of the variables.

6.5. Data analysis

The values of the temperatures measured in the empirical study, the discrete and absolute variables according to descriptive in ranges, maximum and minimum, trend, mean and median valuesshall berecorded.. The VMP and PPI values willbe calculated through the software associated with the Testo® measuring instruments.

A descriptive analysis of the variables obtained shall be carried out. Continuous quantitative variables shall be analysed by the Kolmodorov-Smirnov test and described as mean standard deviation (DS) in case of normal distribution, or as median and range if the distribution does not follow the normal distribution. Qualitative variables shall be described by absolute and relative frequencies. A single-rate analysis shall be performed by observing as variables main dependent temperature and metabolic expenditure. With a 95% confidence interval (p<0.05) quantitative variable means will be contrasted using Student t or Mann-Whitney's U-depending on the sample distribution. The Chi-square test for contingency tables and the Fisher test will be used to assess association of qualitative variables.

A logistic regression model may be established based on the results, analyzing the strength of association in explanatory and predictive terms.

IBM SPSS Stadisticssoftware® v.23 will be used for statistical data analysis

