6.2.4. Sample size

Using the GRANMO sample matingc, Version 7.12 was calculated for the difference of media coupled in energy expenditure at rest of the combination of passive and active external (in two methods, by thermal plate and convective air blanket) versus passive external heating.

Accepting an alpha risk of 0.05 and a beta risk of 0.2 in a bilateral contrast, 34 subjects are required to detect a difference equal to or greater than 0.15 units. A standard deviation of 0.3 is assumed. A 5% tracking loss rate has been estimated.

The difference expected to be found in the resting metabolic expenditure rate of at least 0.1 times the GMB. The increase in baseline metabolic expenditure of these patients in studies with burned patients was 1.4 times with standard deviation of 0.2 - 0.32 times. The sample will be adjusted to the standard deviation values presented in the pilot sample.

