6.4.2 Data collection

For the analysis of thermal comfort, the suppliedam biennage temperatureshall be analysed in the values: minimum of 25oC, 28oC, 31oC as shown in Table 6... The ambient temperature of 33oC is obvious, as it is considered that in combination with the elements of active external overheating average conditions of 33oC are reached. The graphical representation of the

Table 6: Scenario of combination analysis of heating methods

	Ambient temperature		
Registration No.	25oC	28oC	31oC
Thermal plate at 50 cm	1	3	5
Thermal plate at 100 cm	2	4	6
Convective air blanket 38oC			
Convective air blanket 43oC			

measures shall be carried out as represented in *Annexess IV* and *V*.

The convective air blanket, by the heating mechanism, an analysis will be carried out, studying the theoretical effect combined with the ambient temperature.

Sociodemographic and nutritional data of the patient will be collected after acceptance and signature of the informed consent that will be collected in the first days after the patient's entry into the burn unit. Variables will be collected during the night shift (22:00 to 8:00) because there are no scheduled tasks of cures, diagnostic tests or surgical intervention that may alter both the care activity in the unit and the alteration of variables to be collected. Data will be collected for 6 hours from the intervention: evolution of body and central temperature and metabolic expenditure calculated in 24 hours. From the third day after the burn, the 3 heating methods will be applied to study, on three consecutive nights

Study Protocol, Statistical Analysis Plan (SAP), Informed Consent Form (ICF). Version 1.0

Night 1: Ambient temperature 32oC

Night 2: Ambient temperature and combination with thermal plate

Night 3: Ambient temperature and combination with thermal blanket.

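### The main test appears to be chosen from the distribution of the raw levels, although the sized comparison is paired and the alternative branch is an unpaired test

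*Combined protocol and SAP*

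**What the plan says.** Section 6.5 (Data analysis) has two relevant sentences.

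- **Normality check.** "Continuous quantitative variables shall be analysed by the Kolmodorov-Smirnov test"; the sentence goes on to report mean and SD if the distribution is normal, with median and range otherwise. Taken alone, this sentence selects a descriptive summary.
- **Test choice.** A later sentence, at the 0.05 level, says "quantitative variable means will be contrasted using Student t or Mann-Whitney's U-depending on the sample distribution". It does not say which distribution is meant, how it is judged, or whether the t-test is paired.

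The section names metabolic expenditure and temperature as the main dependent variables. It never mentions within-patient differences, a paired test or a signed-rank test.

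The design is paired. Section 6.4.2 says that "the 3 heating methods will be applied to study, on three consecutive nights", and 6.2.3 has metabolic expenditure assessed under all three conditions. Section 6.2.4 sizes the study for the "difference of media coupled in energy expenditure at rest", that is, a difference of paired means between combined and passive heating.

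**The concern.** Three features act together.

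1. **The test is open until the data are seen.** It may differ between the two active methods and between outcomes, so p-values and estimates would not share a common basis.
2. **The distribution examined appears to be the wrong one.** A paired t-test depends on the differences. Spread or skew between patients cancels in the difference, but would still influence a check on the levels.
3. **The non-normal branch discards the pairing.** Mann-Whitney U compares independent groups. A patient population with skewed levels could lose the benefit of the paired design even if the differences were perfectly normal.

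At stake is the power of the main comparison, in a study with only about 32 evaluable patients.

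**Working it through.** **Inputs from 6.2.4.** Two-sided alpha 0.05, power 0.80, difference 0.15, SD 0.3 (read as the SD of the paired differences), 5% loss. Section 6.2.4 also mentions an expected difference of 0.1. I use 0.15 because it is the figure attached to the stated sample size.

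**Reproducing 34.** n = (SD × (z0.975 + z0.80) / difference)² = (0.3 × 2.802 / 0.15)² = 31.4, so 32. With 5% loss, 32 / 0.95 = 33.7, so 34. This confirms a paired calculation: the independent-groups formula gives 63 per group. Paired-t power from the noncentral t is 0.78 at n = 32 and 0.81 at n = 34.

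**Levels versus differences.** Simulation at n = 32, Kolmogorov-Smirnov (K-S) with estimated mean and SD, Lilliefors-corrected at an assumed 5% level:

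| Assumed data | Raw levels rejected | Differences rejected |
|---|---|---|
| Skewed patient levels, normal differences | 59% | 5% |
| Normal baseline, exponential differences | 5% and 14% (two nights) | 81% |

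The check can thus fail in either direction when applied to the levels.

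**Consequence for power.** Assume lognormal patient levels (sigma 0.8), normal differences with mean 0.15 and SD 0.3, n = 32, and within-patient correlation of about 0.6 to 0.74. Read Student t charitably as paired. If normality of the levels is rejected, use Mann-Whitney U; otherwise use the paired t.

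| Simulation | Diverted, corrected K-S | Power of the rule, corrected K-S | Diverted, uncorrected K-S |
|---|---|---|---|
| Run A | 63–73% | 58–69% | 11–17% |
| Run B | 39–55% | 56–67% | 4–8% |

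Always using the paired t gives about 78% in both. Run B is fully specified as follows. Each night is the patient level plus independent normal noise of SD 0.3/√2 = 0.212. The lognormal level is scaled to SD √(0.045 × 0.6/0.4) = 0.26 for correlation 0.6, and √(0.045 × 0.74/0.26) = 0.36 for 0.74. The sample is diverted if either night is rejected, with 20,000 samples per case. The share diverted is sensitive to how night-to-night noise is modelled. The loss is of similar size in both: 78 − 69 = 9 to 78 − 58 = 20 points in A, and 78 − 67 = 11 to 78 − 56 = 22 in B. With uncorrected K-S, run B loses only about 1 to 3 points.

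**Sensitivity of K-S at n = 32** (40,000 samples per case; critical values 0.154 corrected, 0.234 uncorrected):

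| Distribution | Corrected | Uncorrected |
|---|---|---|
| Lognormal, sigma 0.2 | 13% | 0.1% |
| Lognormal, sigma 0.3 | 23% | 0.5% |
| Gamma, shape 4 | 27% | 0.6% |
| t, 5 df | 17% | 0.7% |
| t, 3 df | 36% | 6% |
| Lognormal, sigma 0.5 | 52% | 4.4% |
| Exponential | 81% | 14% |
| Lognormal, sigma 1.0 | 95% | 48% |

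Detection of mild to moderate departures is low: about 13 to 36% corrected and under 7% uncorrected (first five rows). The plan does not say which version will be run.

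**The case against.** **The K-S sentence is descriptive.** It chooses between mean/SD and median/range, for which testing the raw variable is reasonable. The test-choice sentence names no normality test. This stands: the gate is the natural inference, because no other check is offered, but it is not stated. On any reading, though, the test is left to the data and the differences are never mentioned.

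**The paired t-test is fairly robust.** Its simulated type I error at n = 32 is 4.6% for t with 3 df, 7.2% for exponential differences and 11.8% for lognormal (sigma 1.0) differences. So undetected non-normality of the differences matters mainly under strong skew. This also stands. Under this plan a gate that fails to reject leaves the t-test in place, which is the better branch if that test is paired. The loss shown above comes from rejecting on the levels, not from missing non-normality.

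**Stronger readings that a reader might infer, and that are not supported:**

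- *K-S passes almost any data at this sample size.* This is broadly true only of the uncorrected version. The corrected version usually detects strong skew, and the documents do not fix the version.
- *Missing non-normality costs 11 to 14 points of power, while fixing a rank test costs about 2.* That gap is between paired t and Wilcoxon signed-rank, and the plan's alternative is Mann-Whitney U. The ordering also reverses with shape: for exponential differences skewed towards the effect, paired t has about 88% power and signed-rank about 65%.
- *Outlying differences are to be expected in critically ill patients.* The documents give no distribution for the differences and no basis for that expectation.

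**Conclusion.** The point holds as a defect in specification. Section 6.5 leaves the main test to be chosen from the data, apparently from the raw levels. It offers an independent-groups test as the alternative for a comparison that was sized as paired. Where patient levels are skewed and differences are normal, following the rule could cost roughly 9 to 22 points of power from a base of about 78%, if the corrected K-S is used. With the uncorrected version the cost is small.

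These sizes rest on an assumed lognormal shape, correlations of about 0.6 to 0.74, a 5% level for K-S, a t-test that is in fact paired, and an SD of 0.3 that refers to differences. None of the first four is in the documents, and the last is the reading that reproduces 34. The low sensitivity of K-S to mild departures is a further reason not to let it decide the test, but it is secondary. The change is worth making before any data are analysed.

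**What to change.** For the main comparison, delete the distribution-dependent choice and Mann-Whitney U. State in 6.5 that:

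- the primary analysis of energy expenditure, for each active method against passive heating, is a paired t-test on the within-patient differences, or a mixed model over the three nights with patient as a random effect (choose one now), reported with a 95% confidence interval;
- Wilcoxon signed-rank with the Hodges-Lehmann estimate and its 95% confidence interval is a fixed sensitivity analysis, reported whatever the data look like;
- no preliminary normality test changes the primary test.

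K-S may stay for choosing descriptive summaries. A Q-Q plot of the differences or residuals can be shown for information.

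The cost is about two sentences of SAP text. The sample size stays at 34 (32 evaluable), since the existing calculation already assumes a paired analysis. Separately, the 0.15 and 0.1 differences in 6.2.4 need reconciling. At 0.1 the same formula gives (0.3 × 2.802 / 0.1)² = 70.6, so 71, or 75 after 5% loss.

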6.2.1. Target population

Burnt patients receiving treatment in large burnt units that require heating for the maintenance of normothermia and prevention of hypothermia. In 2017, 9186 burn hospitalizations were recorded, with a national incidence of 7 cases per 100,000 inhabitants.

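### Temperature and metabolic expenditure are unranked main outcomes, each tested at p<0.05, although the study is aimed at and sized on energy expenditure alone

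*Combined protocol and SAP*

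**What the plan says.** - **Aim.** Section 6.1 and its Table 5 (stage 2) set out to study how adding active external heating affects metabolic expenditure. Temperature control is not stated as an aim of the patient stage.
- **Sizing.** Section 6.2.4 gives a sample size that "was calculated for the difference of media coupled in energy expenditure at rest". The inputs are "Accepting an alpha risk of 0.05 and a beta risk of 0.2 in a bilateral contrast", an SD of 0.3 and 5% loss, with the result that "34 subjects are required to detect a difference equal to or greater than 0.15 units". No difference or SD is given for temperature.
- **Main outcomes.** Section 6.5 states: "A single-rate analysis shall be performed by observing as variables main dependent temperature and metabolic expenditure". Neither outcome is placed first.
- **Test.** In the same section, "quantitative variable means will be contrasted using Student t or Mann-Whitney's U-depending on the sample distribution", with p<0.05 as the threshold. No adjustment for several outcomes or comparisons is mentioned.
- **Temperature measures.** Section 6.3.1 lists both a surface and a bladder-probe temperature. Section 6.4.2 follows both for 6 hours on each of three consecutive nights. Neither section says which site, or which summary of the 6 hours, is the main temperature variable.
- **Clinical background.** Section 6.2.1 describes the target population as patients who "require heating for the maintenance of normothermia and prevention of hypothermia". No normothermia limits are given.

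**The concern.** The analysis section gives temperature the same standing as the outcome for which the study was designed. This has three consequences.

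1. There are more chances of a false-positive main result. If expenditure shows nothing and temperature crosses p<0.05, the plan as written lets temperature be reported as a main finding.
2. Power for the second main outcome cannot be stated, because the documents give no inputs for it. A null temperature result could not be interpreted.
3. A comparison of means answers a different question from whether patients were kept in a target range. Warming a cold patient and overheating a warm one move the mean the same way, and opposite movements cancel. If normothermia were well maintained on every night, that would appear only as a non-significant difference.

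The choice between surface and bladder readings, and among summaries of 6 hours of data, is also open. That leaves room to select the temperature result after seeing the data.

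**Working it through.** **1. The plan's own figure.** Inputs from section 6.2.4: difference 0.15, SD 0.3 (read as the SD of the paired difference), two-sided alpha 0.05, power 80%, loss 5%.

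n = (SD × (z₀.₉₇₅ + z₀.₈₀) / difference)² = (0.3 × 2.8016 / 0.15)² = 31.4, rounded up to 32. Then 32 / 0.95 = 33.7, rounded up to 34. The stated 34 reproduces, and its inputs are for energy expenditure alone.

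**2. False-positive risk.** Assumptions: no true effect on either outcome; 32 evaluable patients; paired t-tests, matching the paired sizing; two contrasts (each active method against the passive night), which therefore share the passive night.

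| Main outcomes | Contrasts | Chance of at least one p<0.05 |
|---|---|---|
| Expenditure only | 2 | about 9% (simulated) |
| Expenditure and temperature, correlation 0.7 | 2 | about 15% (simulated) |
| Expenditure and temperature, correlation 0 | 2 | about 17% (simulated) |

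As a check, four fully independent tests would give 1 − 0.95⁴ = 18.5%; the shared passive night brings this down. The second outcome adds about 15 − 9 = 6 to 17 − 9 = 8 percentage points. If only one contrast were tested, two independent outcomes would give 1 − 0.95² = 9.75% instead of 5%.

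**3. What a significant temperature result would mean.** With 32 pairs, a paired t-test reaches p<0.05 at a mean shift of t₀.₉₇₅,₃₁ / √32 = 2.04 / 5.66 = 0.36 SD of the differences. This holds in either direction and wherever the mean lies. For assumed SDs of the within-patient difference from 0.3 to 1.0 °C, that is a shift of 0.11 to 0.36 °C. Actual power cannot be computed without a target difference and an SD.

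**4. Why the mean does not settle the range question.** This is an illustration under assumed values: normal distribution, SD 0.8, and a band of 36 to 38 used for arithmetic only. The share in range is Φ((38 − mean)/0.8) − Φ((36 − mean)/0.8).

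| Starting mean | Share in range before | After +0.3 |
|---|---|---|
| 37.5 | 70% | 59% |
| 36.5 | 70% | 77% |

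The same mean shift lowers the share in one case and raises it in the other. The illustration shows ambiguity; it does not predict harm.

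**5. Keeping both outcomes as main instead.** Bonferroni across two outcomes (alpha 0.025) gives (0.3 × 3.083 / 0.15)² = 38.0, rounded up to 39 evaluable, and 39 / 0.95 gives 42. Across two outcomes and two contrasts (alpha 0.0125), (0.3 × 3.339 / 0.15)² = 44.6, rounded up to 45, and 45 / 0.95 gives 48. These sizes are for expenditure; temperature still could not be sized. Section 6.2.2 reports 30 thermal-burn admissions in 2018, so about 30 × 1.5 = 45 over the 18-month recruitment limit, before eligibility is applied.

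**The case against.** The best defence is that the documents already point to expenditure as the leading outcome. The aim and the sizing both say so, and the sentence in section 6.5 reads like a rough translation that may only list the dependent variables for univariable analysis. The study calls itself pre-experimental, and an outcome without its own sample size can still be validly tested. This has force: the evidence for a deliberate co-primary design is thin, and the multiplicity cost is modest. It does not close the gap, because the analysis section is where ranking belongs and, as written, it ranks nothing.

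A reader might infer something stronger: that the plan would count a shift out of normothermia as a success. The documents do not support that. They never call a temperature rise favourable, and a two-sided test only reports a difference. The remark about normothermia in section 6.2.1 describes which patients need heating; it is not the study aim. Share-in-range figures rest on assumed values and go either way.

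Two further points are fair. Section 6.5 is not limited to means: it allows Mann-Whitney and medians for non-normal data, and section 6.3.1 collects a thermoregulation scale (NOC 0800). Nothing ties that scale to the main temperature test, however. Section 6.5 also does not name a paired test, so the figures here follow the paired sizing. Treating the nights as independent samples would change them.

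Temperature in section 6.5 could also be read as the operating temperature of stage 1. But that section summarises the stage 1 temperatures descriptively and separately, so patient temperature is the natural reading.

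**Conclusion.** The concern holds as an unranked-outcomes problem. Two main outcomes at an unadjusted 0.05 raise the chance of at least one false-positive main result from about 9% to about 15 to 17%. This assumes paired tests, 32 evaluable patients, two contrasts sharing the passive night, and an outcome correlation between 0.7 and 0. The 9% baseline belongs to the two-device comparison and would remain after this fix. Temperature has unknown power, an unspecified site and summary, and a test that cannot by itself show whether normothermia was better or worse maintained. The documents do not establish that the plan rewards overheating, and no size can be put on that possibility from the figures they give.

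**What to change.** In section 6.5:

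- Name resting energy expenditure the single primary outcome. This matches sections 6.1 and 6.2.4 and leaves the sample size at 34 on the plan's own inputs.
- Make bladder-probe temperature over the 6-hour window a secondary outcome, with one summary named in advance. Report it as a within-patient mean difference between nights with its confidence interval, and state that it cannot be claimed as a main result.
- Where the recording interval allows, add descriptively the share of readings below, within and above limits that the clinical team sets before analysis.

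The first two changes cost only wording, because the temperature record during heating is already collected under section 6.3.1. The third depends on things the documents do not give: the interval between readings during heating, and the limits themselves. With sparse readings the shares would be coarse, so they are an optional addition. The main downside is that temperature can no longer be claimed as a main result. The alternative in step 5 of the working, two main outcomes with a split alpha, needs 42 to 48 patients from roughly 45 admissions before eligibility, as well as temperature inputs that the plan lacks.

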Clinical Optimization of Ambient Temperature and Heating Methods in Caring in Major Burns Patients

Optimal Heating Temperature in Major Burns Patients

MSN [name]

Universitat Rovira i Virgili
Sanidad Castilla y León
Hospital Universitario Rio Hortega Valladolid
Universidad de Valladolid
[contact]

Study Protocol, Statistical Analysis Plan (SAP), Informed Consent Form (ICF)

Version 1.0

Marchy, 2020

HeatingBurns01- Study Protocol, Statistical Analysis Plan (SAP), Informed Consent Form (ICF)

1. Material and methods

6.1 Design, methodology and justification:

Pre-experimental pre-experimental epidemiological study without control group, in large burnt patients that will evaluate the influence on the metabolic expenditure of the inclusion of active external overheating in the control of ambient temperature adjusted to thermal comfort.. Two methods of active external heating, thermal plate and convective air blanket shall be used. Metabolic expenditure shall be measured by indirect calorimetry in the usual treatment with passive external overheating and post-intervention in the combination of passive and active external warming.

Sand pre-study the combination of passive and active external overheating by measuring the operating temperature in various cases for optimal application, as well as the definition of thermal comfort in the unit of large burns. In this way, two study stages are integrated as shown in *Table 5.*.

Table 5: Study stages Clinical optimization of ambient temperature and heating methods in the care of the patient large burned according to thermal comfort

Stage 1	Stage 2
Empirical study of operating temperature according to the	Quasi-experimental study of large burned patients to study
combination of passive and active external heating methods for the definition of environmental comfort.	the impact on metabolic expenditure of the inclusion of active external overheating in environmental temperature
methods for the definition of environmental connoct.	control

6.2. Population and sample:

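### Section 6.5 names temperature and metabolic expenditure as main outcomes without ranking them, although the aim and the sample size concern energy expenditure alone

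*Combined protocol and SAP*

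**What the plan says.** Section 6.1 describes a study that "will evaluate the influence on the metabolic expenditure of the inclusion of active external overheating". Table 5 repeats this purpose for Stage 2.

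Section 6.2.4 sizes the study on that outcome only: the number of subjects "was calculated for the difference of media coupled in energy expenditure at rest". The error rates are given as "Accepting an alpha risk of 0.05 and a beta risk of 0.2 in a bilateral contrast", with a difference of 0.15 units, a standard deviation of 0.3, 5% losses and 34 subjects.

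Section 6.5 gives the inferential analysis: "A single-rate analysis shall be performed by observing as variables main dependent temperature and metabolic expenditure". The next sentence sets the level for every comparison of means: "With a 95% confidence interval (p<0.05) quantitative variable means will be contrasted", by Student t or Mann-Whitney.

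No section ranks the two outcomes, divides alpha between them or says what counts as a positive result. No section gives an expected difference or standard deviation for temperature. Section 6.3.1 lists two patient temperatures, surface and bladder, and 6.4.2 follows body and central temperature over six hours. Section 6.5 does not say which site or time point it means.

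**The concern.** A sample size with a stated alpha and power implies one test to which those error rates belong. Sections 6.1 and 6.2.4 point to energy expenditure. Section 6.5 puts a second outcome beside it, one for which the study was not sized.

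The two outcomes can disagree. Heating devices act directly on temperature, while their effect on metabolic expenditure is the open question. A clear temperature difference with no difference in expenditure is therefore a plausible result. With no ranking, the report could lead with temperature and leave the stated question in the background. Because site and time point are open, the choice of temperature measure could also be made after the data are seen.

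This is a conflict between outcomes. It would remain if only one active-versus-passive contrast were tested.

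**Working it through.** **Inputs.** From 6.2.4: difference 0.15, SD 0.3 (read as the SD of the paired difference), two-sided alpha 0.05, power 0.80, losses 5%. From 6.5: two main outcomes, tests at 0.05. Assumed, because the documents give none: the correlation between the two test statistics, taken from 0 to 0.8.

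**1. The plan's own figure.**

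n = [SD × (z₀.₉₇₅ + z₀.₈₀) / difference]² = [0.3 × (1.960 + 0.842) / 0.15]² = 31.4, rounded up to 32.

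With losses: 32 / 0.95 = 33.7, rounded up to 34.

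This reproduces the stated 34. The number was built for one energy-expenditure contrast tested at 0.05, with nothing set aside for a second main outcome.

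**2. Chance of at least one false-positive main result.** Two outcomes, one contrast, no true effect on either:

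P = 1 − P(|Z₁| < 1.96 and |Z₂| < 1.96)

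At correlation 0 this is 1 − 0.95² = 0.0975. A false positive on temperature alone (energy expenditure not significant) is P − 0.05, because energy expenditure uses 0.05 by itself.

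| Assumed correlation | At least one false positive | On temperature alone |
|---|---|---|
| 0 | 9.75% | 4.75% |
| 0.5 | 9.1% | 4.1% |
| 0.8 | 7.8% | 2.8% |

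The table uses the bivariate normal. Simulated paired t tests with 32 patients agree (9.7%, about 9%, and 7.7% to 7.9%).

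**3. If both outcomes stayed main, at 0.025 each.**

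n = [0.3 × (2.241 + 0.842) / 0.15]² = 38.02, rounded up to 39; 39 / 0.95 = 41.05, rounded up to 42.

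With 32 evaluable patients, power for the 0.15 difference would fall from 0.78 to 0.68 (noncentral t), or from 0.81 to 0.72 (normal approximation).

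**4. If energy expenditure is the only primary outcome.** Alpha stays at 0.05, so 32 evaluable and 34 enrolled stand as planned.

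No sample size can be worked out for temperature, because the documents give neither a difference nor an SD for it.

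**The case against.** The strongest defence is that the lead outcome can already be identified. The aim and the sample size name energy expenditure, so a claim of success on temperature would contradict both. The text is also a rough translation. The analysis announced in 6.5 is probably meant to be univariate, and the sentence may only list the variables to be examined rather than define formal co-primary outcomes. Temperature is clinically relevant here, since the target population needs heating to maintain normothermia. The study is a single-centre one without a control group, where formal gatekeeping may seem heavy.

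Much of this stands. A reader might infer that under 6.5 a significant result on either outcome makes the trial positive. The documents do not support that, because 6.5 contains no success rule. A reader might also take the whole 8% to 10% as the risk of a false temperature finding, but 5 points of it belong to energy expenditure and are already accepted in 6.2.4. Nor does the error rate describe the case where warming truly raises temperature and leaves expenditure unchanged. That is a problem of interpretation, not a false positive.

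The gap itself is not answered. On any reading of the translation, the sentence names two main dependent variables and ranks neither. Stage 1 does not explain it: 6.5 opens with a separate, descriptive treatment of the empirical-study temperatures, and the sentence at issue comes later, among the inferential tests.

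**Conclusion.** The point holds as an unresolved conflict between 6.5 and sections 6.1 and 6.2.4. Two outcomes are called main, one was sized, and no rule says which decides. What follows is a missing safeguard, not a declared intention to claim success on temperature.

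The numerical effect is moderate: an excess of about 3 to 5 percentage points over the stated 5%. It rests on one active-versus-passive contrast, two outcomes each tested at 0.05, and assumed correlations of 0.8 to 0. Testing plate and blanket separately, or both temperature sites, would add to it. The larger consequence is for interpretation, since the headline outcome is left open until the results are known. The change is worth making because it settles what the trial can conclude at almost no cost.

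**What to change.** In 6.5:

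- Name one primary outcome: the paired difference in resting energy expenditure by indirect calorimetry, tested at two-sided 0.05. State its unit. Section 6.3.1 lists expenditure per day, per m² and per kg, whereas 6.2.4 discusses it as a multiple of basal expenditure. The primary variable should use the unit of 6.2.4.
- Make temperature secondary, with one site and one time point chosen in advance from those already collected. Report it as an estimate with a 95% confidence interval, or test it only after a significant energy-expenditure result.
- Label the other tests exploratory.
- State that a temperature difference without a difference in energy expenditure does not answer the main question positively.

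This is a change of wording. It needs no added patients or measurements, and power for energy expenditure is unchanged at 34 subjects. The small price is that temperature alone cannot support the main conclusion. The alternative of splitting alpha equally would need 42 subjects.
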